### 9.1. Baseline data collection

A specifically designed baseline survey will be used to collect the following information at baseline from all participants, including:

Informed consent

Inclusion/exclusion criteria assessment

Socio-demographics

- Age
- Race/ethnicity
- Gender
- Education
- Economic status
- Occupation
- Insurance information (basic, commercial)

Health and lifestyle information

- Height, weight, body mass index (BMI)
- Blood pressure, heart rate
- Smoking status: Never smokers are defined as those with a lifetime exposure of <1 package/year in their life (excluding passive smoker). Ever smokers (current or former) are defined as those with a lifetime exposure of ≥10 package/year.

Former smokers are those who have stopped smoking for at least 6 months.

Current smokers are those who are currently smoking. Passive smokers are

defined as those with the presence of smokers living in the same household, or co-workers smoking nearby while indoors

- Smoking history including Pack-years of smoking: Number of pack years = (number of cigarettes per day / 20) x number of years smoked, e.g., 10 pack-years means 20 cigarettes per day for 10 years, or 10 cigarettes per day for 20 years)
- Biomass exposure: refer to the biomass exposure questionnaire
- Occupational exposures: Whether had the participant worked in occupations known or suspected to be associated with the risk of COPD  $\geq 6$  months, e.g. organic/inorganic dust, irritant gases, fumes, or vapors chef, traffic police Toxic and harmful jobs (eg.in pollution factory or chemical work, etc)

COPD Medical history (for COPD participants only)

- Disease duration
- Treatment history (e.g. the time of initiating maintenance treatment, current treatment)
- Number of exacerbations in the previous 12 months and 24 months
- Number of moderate and severe exacerbations in the previous 12 months and 24 months and their management with oral corticosteroids and/or antibiotics and/or hospitalization
- Family history of COPD or other respiratory diseases

Lower respiratory infections including chest colds (for chronic bronchitis patients only)

Medical history (including previous asthma history)

Current co-morbid conditions and childhood respiratory disease

Concomitant medications: Respiratory medications, antibiotics, oral steroids, anti-diabetic, anti-hypertension gastroesophageal reflux disease (GERD) therapy, cardiovascular disease therapy and whether taking traditional Chinese medicines

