## 5.5. Examination of Covariates, Other Strata and Subgroups

### 5.5.1. Covariates and Other Strata

The potential covariates for statistical analyses may include type of subjects (i.e. GOLD I-IV, chronic bronchitis, healthy control), gender, smoking status, baseline FEV1, count of COPD exacerbations in the previous 12 months from baseline. For analyses where a baseline value (of the analysis variable) is available this will also be included as a covariate in model-based analyses, and baseline by visit interaction may be included depending on the model. [CC1]

[REDACTED]

[REDACTED]

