COPD Exacerbation History

 
• Individual exacerbations during the 12/24 months prior to Screening and during the study were to be collected on the eCRF by the investigator
 
• COPD exacerbations with onset date on or after the date of Screening will not be counted in the counts of number of exacerbations in the past year; all other exacerbations recorded on the eCRF will be included in the counts, even if onset/resolution dates were missing or earlier than the start of the exact 12 month period prior to Screening
 
• Number of COPD exacerbations reported in the past year prior to Screening will be summarised according to three categories: moderate COPD exacerbation, severe COPD exacerbation and moderate/severe COPD exacerbation.
 
• Moderate COPD exacerbations are defined as exacerbation that required treatment with oral/systemic corticosteroids and/or antibiotics (not involving hospitalisation).
 
• Severe COPD exacerbations are defined as exacerbations that required in-patient hospitalisation.
 

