**Digital Physical Activity**

- SEDENTARY - Little to no activity monitored. This could be due to minimal movement, sitting, resting, or sleeping.
- ACTIVE - Some activity monitored. A brisk walk could achieve this intensity.
- HIGHLY\_ACTIVE - High activity monitored. Running or speed walking could achieve this intensity.

• Below is a template of how activity information is summarized for site personnel in Rave EDC

CRF Component	Value Format	Calculation	Example Values
Date	Text	Date of log line record	26 MAR 2015
Sync Date/Time	Text	Date and time data was synced to Garmin	26 MAR 2015 14:00
Daily Steps Walked	Numeric	Total # of steps in routine data objects for a subject's day (timezone is subject's)	2240
Sedentary Minutes	Numeric	Total # of minutes in routine data objects for a subject's day (timezone is subject's) with intensity parameter = sedentary	438
% of time sedentary	Numeric	Total # of minutes in routine data objects for a subject's day (timezone is subject's) with intensity parameter = sedentary divided by 1440 minutes (total # of minutes per day)	85.32
Active Minutes	Numeric	Total # of minutes in routine data objects for a subject's day (timezone is subject's) with intensity parameter = active	74
% of time active	Numeric	Total # of minutes in routine data objects for a subject's day (timezone is subject's) with intensity parameter = active divided by 1440 minutes (total # of minutes per day)	14.47
Very Active Minutes	Numeric	Total # of minutes in routine data objects for a subject's day (timezone is subject's) with intensity parameter = very active	1
% of time very active	Numeric	Total # of minutes in routine data objects for a subject's day (timezone is subject's) with intensity parameter = very active divided by 1440 minutes (total # of minutes per day)	0.20

Digital Physical Activity			
Total Daily Minutes Sleep	Numeric	Total # of minutes in sleep data objects for a subject's day (timezone is subject's)	362

Phenotype	
Exacerbator	

 
Exacerbator is categorized based on the number of exacerbations patients have in the past:           
 
Never
 
Occasional (1 in the last 2 years)
 
Yearly (1 each year in the last 2 years)
 
 
 
Frequent (<math>\geq 2</math> in the previous year)
 
	
Chronic mucus hypersecretion (CMH)	

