
 
Smoking status: Never smokers are defined as those with a lifetime exposure of <1 package/year in their life (excluding passive smoker). Ever smokers (current or former) are defined as those with a lifetime exposure of <math>\geq 10</math> package/year. Former smokers are those who have stopped smoking for at least 6 months. Current smokers are those who are currently smoking. Passive smokers are defined as those with the presence of smokers living in the same household, or co-workers smoking nearby while indoors
 
Smoking status will be reassessed at each scheduled clinic visit evaluated by participants' self-report (e.g. never smoker, current smoker, former smoker).
 
Smoking history including Pack-years of smoking: Number of pack years (number of cigarettes per day / 20) x number of years smoked, e.g., 10 packyears means 20 cigarettes per day for 10 years, or 10 cigarettes per day for 20 years)
 

COPD Exacerbation History

 
Individual exacerbations during the 12/24 months prior to Screening and during the study were to be collected on the eCRF by the investigator
 
COPD exacerbations with onset date on or after the date of Screening will not be counted in the counts of number of exacerbations in the past year; all other exacerbations recorded on the eCRF will be included in the counts, even if onset/resolution dates were missing or earlier than the start of the exact 12 month period prior to Screening
 
Number of COPD exacerbations reported in the past year prior to Screening will be summarised according to three categories: moderate COPD exacerbation, severe COPD exacerbation and moderate/severe COPD exacerbation.
 
Moderate COPD exacerbations are defined as exacerbation that required treatment with oral/systemic corticosteroids and/or antibiotics (not involving hospitalisation).
 
Severe COPD exacerbations are defined as exacerbations that required in-patient hospitalisation.
 
Total number of moderate/severe COPD exacerbations are defined as total numbers of moderate and severe COPD exacerbation for each subject.
 

Baseline Lung Function
Reversibility
Reversibility will be calculated as follows: (Highest post-bronchodilator FEV 1 – Highest pre-bronchodilator FEV 1 )*100/(Highest post-bronchodilator)
GOLD Grade 1-4 at Screening

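### SAP 17.5.2 sets no lower date limit on the past-year exacerbation count, so the baseline past-year summaries can take in up to 24 months of events

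*SAP*

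**What the plan says.** SAP 17.5.2, under COPD Exacerbation History, makes four statements that matter here. The appended RAP carries the same text in its 12.5.2.

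- Collection: "Individual exacerbations during the 12/24 months prior to Screening and during the study were to be collected on the eCRF by the investigator".
- The only exclusion, which applies to the past-year count: "COPD exacerbations with onset date on or after the date of Screening will not be counted in the counts of number of exacerbations in the" (the sentence goes on to name that year).
- The inclusion rule: "all other exacerbations recorded on the eCRF will be included in the counts, even if onset/resolution dates were missing or earlier than the start" (meaning before the 12-month window preceding Screening opens).
- The output: "Number of COPD exacerbations reported in the past year prior to Screening will be summarised according to three categories", namely moderate, severe, and the two combined.

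Three other places use or collect exacerbation history. Protocol 9.1 records "Number of exacerbations in the previous 12 months and 24 months", and also the moderate and severe numbers over the same two windows. SAP 5.5.1 lists "count of COPD exacerbations in the previous 12 months from baseline" among its potential covariates. SAP 13.1 and 17.5.3 sort COPD participants into Never, Occasional, Yearly and Frequent exacerbators. In 17.5.3, Yearly means one event in each of the last two years, and Frequent means at least two in the previous year.

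**The concern.** Keeping every pre-Screening event is harmless when the eCRF asks about 12 months only, because the older events are then a few misdated ones near the boundary. Here the eCRF look-back extends to 24 months. The rule has an upper date limit (Screening) and no lower one, so it admits a whole second year of events into a figure labelled past year.

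At stake first is the baseline description. The past-year moderate, severe and combined counts would be overstated, and any comparison of them with a true 12-month history from another cohort would be misleading. At stake second, and only conditionally, are the 12-month covariate and the exacerbator phenotype, should they be programmed from the same count.

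**Working it through.** The documents state no figure for this rule, so there is none to reproduce. The check has two parts.

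**1. Apply the rule to every history.** Let y1 be the number of events in months 0–12 before Screening and y2 the number in months 12–24.

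- True past-year count: y1.
- Count under 17.5.2 as written: y1 + y2.

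The phenotype column assumes that the count as written is also used for the phenotype.

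| (y1, y2) | True past-year count | Count as written | Phenotype with true counts | Phenotype with count as written |
|---|---|---|---|---|
| (0, 0) | 0 | 0 | Never | Never |
| (0, 1) | 0 | 1 | Occasional | Occasional |
| (1, 0) | 1 | 1 | Occasional | Occasional |
| (1, 1) | 1 | 2 | Yearly | Frequent |
| (0, 2) | 0 | 2 | none fits as worded | Frequent |
| (1, 2) | 1 | 3 | none fits as worded | Frequent |
| (2, 0) | 2 | 2 | Frequent | Frequent |

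The counts go wrong whenever y2 > 0. A participant whose only event was 18 months ago goes from 0 to 1 past-year events but stays Occasional. The phenotype changes at (1, 1), (0, 2) and (1, 2).

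**2. Illustrate the size.** With mean event numbers m1 and m2 in the two years, the ratio of the mean as written to the true mean is (m1 + m2)/m1 = 1 + m2/m1. If the rate is constant, m2 = m1 and the ratio is 2. If fewer events are recalled from the older year, the ratio is smaller; for example, m2 = 0.5 × m1 gives 1.5.

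For the share with at least two past-year events, take a constant rate L per year. The true mean is L and the mean as written is 2L.

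- Poisson with mean m: P(N ≥ 2) = 1 − e^(−m)(1 + m).
- Negative binomial with shape 1 and mean m: P(N ≥ 2) = [m/(1 + m)]².

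| Assumed L (per year) | Model | True | As written |
|---|---|---|---|
| 0.2 | Poisson | 1.8% | 6.2% |
| 0.3 | Poisson | 3.7% | 12.2% |
| 0.5 | Poisson | 9.0% | 26.4% |
| 1.0 | Poisson | 26.4% | 59.4% |
| 0.5 | Negative binomial | 11.1% | 25.0% |
| 1.0 | Negative binomial | 25.0% | 44.4% |

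Worked line, Poisson at L = 0.5: true 1 − e^(−0.5) × 1.5 = 0.090; as written 1 − e^(−1) × 2 = 0.264.

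The share with any past-year event, 1 − e^(−m), also moves: at L = 0.2 from 18.1% to 33.0%, and at L = 0.5 from 39.3% to 63.2%.

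**The case against.** The strongest reply is that the sentence was meant as a tolerance. An event reported for the past year is kept although its recalled date is missing or falls slightly outside the window, and the next statement in 17.5.2 does speak of events reported in the past year. If the eCRF separates 12-month from 24-month entries, that reading would work. The eCRF is not among the documents, so this cannot be settled. But the text sets no bound on the tolerance, and it follows directly on a statement that the look-back is 12/24 months. A programmer who follows it as written gets the longer count. The appended RAP shows that the wording was carried forward; it is not independent support for either reading.

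The second reply concerns consequences, and it largely stands. A reader might infer that Yearly exacerbators will be reported as Frequent. The documents do not support that as a certainty. Sections 13.1 and 17.5.3 state their own windows and do not cite this count. Yearly needs a year-by-year split that the count as written cannot supply, and Protocol 9.1 collects 12- and 24-month numbers that could supply it. The covariate in 5.5.1 also states its own window and is only a potential one. The models in SAP 7.1 and 8.1 name an exacerbation history or count without referring to 17.5.2.

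Two further inferences should be set aside. The rule does not count every event on the eCRF, since events on or after Screening are excluded. The history subgroup in SAP 5.5.2 (any or none in the preceding years) and the two-year exacerbator definition in Protocol 5.2 do not need a past-year count and are unaffected.

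Finally, the rates above are assumptions. Amendment 2 describes a mainly mild-to-moderate population with fewer treated exacerbations, and 17.5.2 counts treated or hospitalised events, so the lower rows of assumed rates are the more relevant ones.

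**Conclusion.** The rule is wrong as written for a baseline summary. The past-year moderate, severe and moderate/severe counts include every pre-Screening event on the eCRF, and undated ones, and so cover up to 24 months. At a constant rate the mean doubles; at assumed Poisson rates of 0.2 to 0.5 per year, the share with two or more events is roughly three times too high (6.2/1.8 = 3.4; 26.4/9.0 = 2.9). These sizes rest on an assumed rate, on equal rates in the two years and on equally complete recall.

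Effects on the 5.5.1 covariate and the exacerbator phenotype are conditional on the same count being used there, which the SAP neither states nor rules out. FEV1 decline, the on-study exacerbation rate as an outcome, and the sample size do not depend on it. The study is mainly descriptive with no formal inference. This should be corrected before final programming; it does not threaten the study's main results.

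**What to change.** Amend SAP 17.5.2 as follows.

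1. Delete the clause, beginning at 'or earlier', that admits events dated before the 12-month period.
2. Limit the past-year count to events with onset within 12 months before Screening, and state the day count. Under the protocol's convention that a month is 30 days (Schedule of Activities, footnote 4), 12 months is 12 × 30 = 360 days and 24 months is 720 days.
3. Define a separate count for months 12–24.
4. Assign an event with a missing onset date to the 12- or 24-month eCRF item under which it was reported, if the eCRF allows this. Otherwise use the separately collected 12- and 24-month numbers from Protocol 9.1.
5. Name these counts as the source for the 5.5.1 covariate and the 13.1/17.5.3 phenotype.

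The 5.5.2 subgroup needs no change. The cost is a short SAP edit, a date filter in programming, and a check of how the eCRF records the two windows. No new data are required.

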**COPD Exacerbation History**

- Total number of moderate/severe COPD exacerbations are defined as total numbers of moderate and severe COPD exacerbation for each subject.

**Baseline Lung Function****Reversibility**

Reversibility will be calculated as follows:

(Highest post-bronchodilator FEV1 – Highest pre-bronchodilator FEV1) \* 100 / (Highest post-bronchodilator)

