Patient reported outcomes: CAT, SGRQ-C and mMRC, CAPTURE

Spirometry (pre- and post-bronchodilator)

- FEV1
- Forced vital capacity (FVC) & Percent Predicted FVC and FEV1/FVC ratio & Percent Predicted FEV1/FVC
- Forced expiratory volume in 6 seconds (FEV6)
- Forced expiratory flow between 25% and 75% of vital capacity (FEF 25-75) & Percent Predicted FEF 25-75, Forced Expiratory Flow 25% (FEF25), Forced Expiratory Flow 50% (FEF50) and Forced Expiratory Flow 75% (FEF75)
- Peak Expiratory Flow (PEF) & Percent Predicted PEF, time to Peak Expiratory Flow (tPEF) and Maximal Mid-Expiratory Flow (MMEF)
- Forced Expiratory Time (FET) and Volume back extrapolation (VEXT)

- FEV1 percent of predicted and reversibility test
  - Reversibility will be assessed at Visit 1 (baseline) by measurement of FEV1 before and 10 to 30 minutes after administration of a short-acting bronchodilator (e.g. 400µg β2-agonist or up to 160µg anticholinergic). Prior to testing, the patients should not have taken inhaled short-acting bronchodilators in the previous six hours, long-acting bronchodilator in the previous 12 hours or sustained-release theophylline in the previous 24 hours.
  - Reversibility will be calculated as follows: % Reversibility =  
$$\frac{\text{Highest post - bronchodilator FEV}_1 - \text{Highest pre - bronchodilator FEV}_1}{\text{Highest pre - bronchodilator FEV}_1} \times 100$$

Collection of blood samples for protocol defined analysis (plasma fibrinogen and hsCRP, total and differential blood cell count)

In addition, the following assessments will be conducted among the Biomarker & Digital sub-cohort participants only:

Blood biomarkers (including serum sRAGE, CC16, IP-10, HbA1c)

Sputum sample collection for protocol defined analyses (microbiome through molecular methods, cytology)

Lung HRCT

Issue and training in use of electronic diary: EXACT questionnaire (start after clinic visit at baseline)

Digital steps (start after clinic visit at baseline)

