## 2. SUMMARY OF KEY PROTOCOL INFORMATION

### 2.1. Changes to the Protocol Defined Statistical Analysis Plan

There were changes to the original planned statistical analyses specified in the protocol amendment 02 (Dated:17JUN2021) of study 208630 [TMF-13816843].

The definition of population will follow the description of SAP, to better fit the study purpose. HRU population added due to data collection status.

Considering the COVID lockdown impact, analysis window for the 3 post-baseline visits (Month 6, Month 18, Month 30) will be changed to  $\pm 90$  days.

Rate of change (decline) in CAT score analysis will be performed in further post-hoc analysis.

Phenotype analyses will be descriptive only, and further analyses of phenotype may be performed post hoc and based on separate documents.

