## 2.3. Study Design

## 2.4. Statistical Hypotheses / Statistical Analyses

This study is mainly descriptive with no formal inference associated with the study objectives. Nominal P-value may be provided as reference. 2-sided 95% confidence intervals will accompany all effect estimates.

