## 8. CLINICAL FEATURE ANALYSES

### 8.1. Spirometry

Summary of pre- and post-bronchodilator spirometry (including FEV1, FVC, FEV1/FVC Ratio, FEV6, FEF25-75, FEV1 percent of predicted test, FEV1 percent of reversibility test, and predicted forced vital capacity) will be provided by arm.

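### SAP 17.5.2 divides reversibility by the post-bronchodilator value, Protocol 9.1 by pre-bronchodilator FEV1; the change is undeclared and lowers every non-zero value in one descriptive summary

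*SAP*

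**What the plan says.** Protocol 9.1 (Baseline data collection) specifies reversibility testing at Visit 1 and introduces its formula with "Reversibility will be calculated as follows: % Reversibility". The numerator is the highest post-bronchodilator FEV1 minus the highest pre-bronchodilator FEV1. The denominator is the highest pre-bronchodilator FEV1, and the result is multiplied by 100.

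SAP 17.5.2 (Study Population, Baseline Lung Function) gives the same numerator but closes with "100 / (Highest post-bronchodilator". The word FEV1 is absent after the denominator. The appended RAP has the same derivation in its section 12.5.2, ending "100/(Highest post-bronchodilator".

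SAP 2.1 states that "There were changes to the original planned statistical analyses specified in the protocol amendment 02" and then lists them: population definitions and the added HRU population, the ±90-day analysis window, the move of the CAT slope to post-hoc analysis, and the restriction of phenotype analyses to description. Reversibility is not on the list.

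SAP 8.1 includes "FEV1 percent of reversibility test" among the spirometry measures to be summarised by arm.

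**The concern.** The two documents define one named quantity in two ways, and both definitions cannot be followed. Because SAP 2.1 declares no change, a reader of the reversibility summary would assume the protocol definition. A programmer working from the derivation appendix would produce the other one.

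The discrepancy runs in one direction. It does not average out over participants, and for positive responses it grows with the size of the response, so the upper end of the distribution is compressed most. In a mainly descriptive study the summaries are themselves the output, so a baseline variable on an unannounced denominator is a reporting error even though no test depends on it.

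**Working it through.** The plan gives no numerical reversibility figure to reproduce, so the check is on the formulas.

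**Inputs**
- Protocol 9.1: denominator is highest pre-bronchodilator FEV1.
- SAP 17.5.2 (and RAP 12.5.2): denominator is the highest post-bronchodilator value, taken here to mean FEV1.
- Response sizes: illustrative, because the documents contain no participant values.

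**Algebra.** Let d = post − pre.
- Protocol: R = 100 × d/pre
- SAP: S = 100 × d/post
- Difference: S − R = 100 × d × (pre − post)/(pre × post) = −100 × d²/(pre × post)

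FEV1 is positive, so the difference is never positive and is zero only when d = 0. Since post = pre × (1 + R/100), S = R/(1 + R/100), and the shortfall in percentage points is R²/(100 + R).

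**One case in full.** With pre = 1.5 L and post = 1.8 L, d = 0.3 L. The protocol gives 0.3/1.5 = 20.0%; the SAP gives 0.3/1.8 = 16.7%.

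**Range of responses**

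| Protocol value R | SAP value S | Shortfall R²/(100 + R), points |
|---|---|---|
| −5% | −5.26% | 25/95 = 0.26 |
| 0% | 0% | 0 |
| 5% | 4.76% | 25/105 = 0.24 |
| 10% | 9.09% | 100/110 = 0.91 |
| 12% | 10.71% | 144/112 = 1.29 |
| 15% | 13.04% | 225/115 = 1.96 |
| 20% | 16.67% | 400/120 = 3.33 |
| 30% | 23.08% | 900/130 = 6.92 |

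The results do not depend on the level of pre-bronchodilator FEV1: values of 1.0, 1.5 and 2.0 L give the same table. For a negative response, lower means more negative, so larger in magnitude.

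**Where the variable is used in the current SAP.** It appears in the by-arm summary of section 8.1. It is not in the visible covariate list (5.5.1), the subgroup list (5.5.2), the negative binomial model (7.1), the MMRM or random coefficients models (8.1), or the phenotypes and endotypes (13.1, 13.2). Asthma-COPD overlap is defined there by physician-diagnosed asthma at age 40 or younger. The inclusion and exclusion criteria in Protocol 6.1 and 6.2 do not use reversibility either.

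**The case against.** The best case against acting is that very little depends on this variable. SAP 2.4 says "This study is mainly descriptive with no formal inference associated with the study objectives", and reversibility is not among the endpoints in SAP 2.2. The transformation preserves the ordering of participants, and the shortfall is below one point at responses of 10% or less. No document says how common responses of 20% to 30% are. Pre- and post-bronchodilator FEV1 are both collected, so the protocol value can be recomputed at any time. The missing FEV1 in the SAP denominator suggests a transcription slip that the code may not share, and no program or output is available to show what was done. The tabulated value might also come straight from the spirometer or the eCRF; the documents do not say. All of this stands, and it limits the size of the point. It does not reconcile the two formulas.

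Four stronger readings are tempting, and the documents do not support them.
- **Every reported value is too low.** Zero change is unaffected, and what was programmed is unknown.
- **Participants are misclassified around 12%.** It is true that 0.12/(1 − 0.12) = 13.6% would be needed under the protocol formula to be reported as 12%, but neither document sets a reversibility cut-off or responder category.
- **Comparison with other cohorts is damaged.** The first objective concerns predictors of progression found in Western cohorts; no section names reversibility for that purpose.
- **Subgroup analyses are affected.** The appended RAP (section 7.4.1) names baseline reversibility in its subgroup text, but the subgroup list in SAP 5.5.2 does not carry it over.

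**Conclusion.** The point holds as an undeclared mismatch of definitions between protocol and SAP. If SAP 17.5.2 is programmed literally, every non-zero reversibility value is lower than the protocol-defined value by R²/(100 + R) percentage points, or 1.29 points at 12% and 6.92 points at 30%. The consequence is confined to a descriptive baseline summary. Eligibility, GOLD grade, the FEV1 and FVC endpoints, and the models and subgroups listed in the current SAP are unaffected.

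The conclusion rests on three assumptions: that the protocol formula is the reference, because SAP 2.1 declares no departure from it; that the SAP denominator means post-bronchodilator FEV1; and that the summary is derived by the SAP formula. If the summary takes a value supplied from elsewhere, the table may be right, but the SAP text would still need to match it. The point is small but worth correcting.

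**What to change.** In SAP 17.5.2, change the denominator to the highest pre-bronchodilator FEV1, naming the variable in full, so that it matches Protocol 9.1. Check the derivation code against the corrected text. If baseline tables were already produced under the RAP, whose Table 3 also lists the reversibility test, check those too.

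Should the post-bronchodilator denominator have been intended after all, SAP 2.1 should declare and justify it and the table should be labelled accordingly.

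The cost is one line of SAP wording, a check of the code, and one line of code if it followed the SAP. No new data are needed, because both FEV1 values are already collected, and study conduct does not change.
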